7.1.2 Exclusion Criteria

To be eligible for enrollment, a patient must not meet any of the following exclusion criteria at the time of the first study-specified biospecimen collection (Time 0):

1. Patient/LAR declines participation.
2. Acute cardiovascular or pulmonary organ dysfunction (inclusion criterion #3) has been present for > 48 hours.
3. Patient has been in an eligible unit (inclusion criterion #2) for more than 120 hours (five days).
4. Patient is no longer expected to meet the acute cardiovascular or pulmonary organ dysfunction inclusion criterion (inclusion criterion #3) 24 hours after enrollment.
5. Patient desires comfort measures only.
6. Patient is a prisoner.

7. Patient had out-of-hospital cardiac arrest leading to this hospitalization.
8. Residence immediately before this hospitalization in a long-term acute care facility.
9. Presence of tracheostomy for respiratory failure.
10. Home invasive mechanical ventilation or non-invasive ventilation (except patients with non-invasive ventilation prescribed as a treatment for a sleep disorder may participate).
11. Suspected cause of the patient's acute cardiovascular and/or pulmonary dysfunction (inclusion criterion #3) is an alternative condition (not ARDS, pneumonia, or sepsis), including but not limited to the list below:
 - i) Drug overdose (without aspiration, lung injury, pneumonia, or infection).
 - ii) Trauma (without aspiration, pneumonia, or infection).
 - iii) Chronic lung disease without suspected infection, aspiration, or inflammation.
 - iv) Asthma, COPD, sarcoidosis, interstitial lung disease, neuromuscular respiratory failure.
 - v) Status epilepticus.
 - vi) Acute pulmonary embolism.
 - vii) Acute decompensated heart failure.
 - viii) Diabetic ketoacidosis.
 - ix) Acute stroke or intracranial hemorrhage.
 - x) Acute bleeding (GI bleeding, post-procedural bleeding, hemolysis).
 - xi) Cytokine release syndrome due to chemotherapy.
12. Inability or unwillingness to complete study-specified blood draws, for example, due to local policies about hemoglobin thresholds for research blood draws.

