7.1 Eligibility Criteria

7.1.1 Inclusion Criteria

To be eligible for enrollment, a patient must meet all the following inclusion criteria at the time of the first study-specified biospecimen collection (Time 0):

1. Age \geq 18 years old.

2. Admitted (or planned to be admitted) to an ICU or other in-patient hospital location where IV vasopressors or advanced respiratory support (invasive mechanical ventilation, non-invasive ventilation, or high flow nasal cannula) are routinely provided (referred to as an “eligible unit.”)
3. Acute cardiovascular or pulmonary organ dysfunction defined by meeting at least one of the two criteria below:
 - i) New receipt of invasive mechanical ventilation, non-invasive ventilation, high flow nasal cannula, or supplemental oxygen at a flow rate of ≥ 6 lpm for acute hypoxemia.
 - Patients who use chronic oxygen therapy are eligible to participate if they are receiving at least 6 lpm higher than their baseline oxygen requirement (e.g., a patient on 3 lpm O₂ at baseline is eligible if they require ≥ 9 lpm for hypoxemia) or are started on advanced respiratory support (invasive mechanical ventilation, non-invasive ventilation, or high flow nasal cannula).
 - ii) Receipt of intravenous infusion of a vasopressor medication for at least one hour.
4. Acute cardiovascular or pulmonary organ dysfunction (inclusion criterion #3) is attributed to an acute inflammatory condition, including but not limited to any of the following:
 - i) Any infection including pneumonia.
 - ii) Aspiration pneumonitis.
 - iii) Pancreatitis.
 - iv) Auto-inflammatory condition such as:
 - a. Hemophagocytic lymphohistiocytosis.
 - b. Suspected acute rheumatologic or auto-immune disease with pulmonary or cardiovascular manifestations.
 - c. Suspected cryptogenic organizing pneumonia presenting acutely.
 - d. Suspected diffuse alveolar hemorrhage.
 - e. Suspected acute anaphylaxis.
 - f. Suspected acute pulmonary drug toxicity.

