7.1.3 Rationale for eligibility criteria

The goal is to enroll patients with acute cardiopulmonary dysfunction that is due to either (a) ARDS, pneumonia, or sepsis, or (b) an acute inflammatory condition that places patients at high risk for short-term development of ARDS, pneumonia, or sepsis. Patients with common critical care conditions that may result in acute cardiopulmonary dysfunction, but which have established pathophysiologic mechanisms distinct from ARDS, pneumonia, and sepsis will be excluded. This approach will optimize the ability to understand the pathophysiology of ARDS, pneumonia, and sepsis, whereas an approach that limited enrollment to patients who meet the historical syndrome definitions would limit our ability to identify new, meaningful phenotypes. In addition, this approach recognizes the difficulty in making definitive clinical diagnosis of historical syndromes (ARDS, pneumonia, and sepsis) at the time of enrollment among critically ill patients. By taking this approach to inclusion criteria, the APS Consortium is expected to further improve our ability to make diagnoses in real time.

Potential participants of all sexes, genders, races, ethnicities, language proficiencies, and nationalities are invited to participate. Enrollment in the cohort will not be limited by the language(s) spoken by the

participant. Individual components of APS studies, such as long-term outcome surveys, may be limited to participants who speak certain languages to ensure adequacy of data collection for those components. All adult patients across the age span are invited to participate; pediatric participants are not the focus of this project and will not be enrolled.

Pregnant individuals are eligible to participate in the APS cohort because pregnant patients experience APS syndromes at rates higher than the general population of similar age, and there is no strong rationale to exclude such participants. The risks of the procedures in this study are not greater for pregnant participants than for other participants. Due to potential risks to a fetus posed by study procedures that are greater than minimal risk, study procedures for pregnant participants will be limited to procedures that are not greater than minimal risk. The altered schedule of procedures for pregnant participants is detailed in the schedule of events section of this protocol.

Prisoners are excluded because there is concern that their participation may not be fully voluntary.

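### The stem of exclusion criterion 11, read literally, bars the at-risk inflammatory patients without a suspected syndrome whom inclusion criterion 4 and the rationale say are to be enrolled

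*Protocol*

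**What the plan says.** Protocol section 7.1.1 requires every inclusion criterion to be met. Criterion 3 asks for acute cardiovascular or pulmonary dysfunction, and one of its two routes is cardiovascular alone: "Receipt of intravenous infusion of a vasopressor medication for at least one hour". Criterion 4 asks that this dysfunction "is attributed to an acute inflammatory condition, including but not limited to any of the following". Infection is one entry on that list. The others include aspiration pneumonitis, pancreatitis, hemophagocytic lymphohistiocytosis, diffuse alveolar hemorrhage, pulmonary drug toxicity and "Suspected acute anaphylaxis".

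Section 7.1.2 says that "a patient must not meet any of the following exclusion criteria at the time of the first study-specified biospecimen collection (Time 0"). Criterion 11 excludes a patient when the suspected cause of the dysfunction "is an alternative condition (not ARDS, pneumonia, or sepsis), including but not limited to the list below". Eleven items follow.

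Section 7.1.3 sets two enrolment goals. The first is patients with ARDS, pneumonia or sepsis. The second is "b) an acute inflammatory condition that places patients at high risk for short-term development of ARDS, pneumonia, or sepsis". It adds that restricting enrolment to the historical definitions would make it harder to find new phenotypes. Section 6 likewise counts conditions at high risk of progressing to one of the syndromes as part of the study population.

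**The concern.** Criterion 11 defines an alternative condition by reference to the three syndromes alone, its list is open-ended, and it makes no exception for the conditions that criterion 4 admits. Since one exclusion is enough to make a patient ineligible, the exclusion overrides the inclusion wherever the two meet. They meet in patients with a non-infectious inflammatory condition in whom none of the syndromes is yet suspected, which is the second enrolment goal.

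At stake is who enters a cohort built for phenotype discovery. A site that applies criterion 11 as written and a site that applies the rationale would decide differently on the same patient. Patients not enrolled for this reason cannot be recovered at analysis.

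**Working it through.** No arithmetic applies. The check sets the eligibility clauses side by side and runs patients through them.

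**Patient A: suspected anaphylaxis, vasopressor infusion for more than one hour, no suspected ARDS, pneumonia or sepsis.**
- Inclusion 3: met through the vasopressor route.
- Inclusion 4: met, because anaphylaxis is named.
- Section 7.1.3, second goal: the patient has an acute inflammatory condition of the kind criterion 4 lists, so the rationale points to enrolment.
- Exclusion 11: the suspected cause is not one of the three syndromes, so the stem applies. Anaphylaxis is not among items i to xi, but the list is open-ended, so its absence does not protect the patient.
- Result: admitted by 7.1.1 and 7.1.3, barred by 7.1.2.

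**Patient B: uninfected pancreatitis on vasopressors, no suspected ARDS.** The steps and the result are the same.

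**Patient C: pancreatitis or aspiration with suspected ARDS.** Inclusion 3 and 4 are met. The suspected cause falls within ARDS, so the stem of exclusion 11 does not apply. Section 7.2.2 expects ARDS from non-infectious insults to be enrolled, and section 8.1.3 names aspiration and pancreatitis as ARDS precipitants. There is no conflict.

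The conflict is therefore confined to patients like A and B.

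**Consistency with the rest of the protocol.**
- Section 7.2.2 says most, not all, enrolled patients will have one of the syndromes at some point in the stay.
- Section 7.3 sets time zero at the first biospecimen, whenever a syndrome develops.
- Section 16.3.7 expects ventilated participants with causes of respiratory failure other than the three syndromes.
- Section 7.1.3 says the exclusions are for common conditions whose mechanisms are established and differ from those of the syndromes. That test is narrower than the one in the stem of criterion 11.

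These passages assume the broader population. The stem of criterion 11 alone describes the narrower one.

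**The case against.** The strongest reply is that the intent is plain. Section 7.1.3 stands directly after the exclusions and says which conditions they target. None of the eleven listed items is named in inclusion 4. Items i to iii even spare patients with suspected aspiration, which is broader than the three syndromes. Read with the rationale, an alternative condition has a workable meaning. This stands as evidence of intent and lowers the practical risk. It does not change the criterion, and the list does not settle how far the stem reaches: item xi excludes cytokine release syndrome due to chemotherapy, so criterion 11 does cover some conditions that a site could regard as inflammatory.

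A second reply is that the Steering Committee reviews participant characteristics overall and by site at least quarterly, including the distribution of syndromes (section 7.2.1), and that section 12.2 asks analysts to consider the multi-level structure. Both would help to detect or handle differences between sites. Neither corrects the wording. Divergence between sites is a plausible consequence, but the protocol does not show that it has happened.

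Three stronger readings are tempting and are not supported.
- **That criterion 11 removes all patients with non-infectious inflammatory conditions.** Patient C shows otherwise.
- **That section 16.3.8 bounds the loss.** It expects 1,050 of 1,500 ventilated patients to have sepsis, so 1,500 − 1,050 = 450 (450/1,500 = 30%) would not. Those 450 are patients expected to be enrolled, not lost. Some will have ARDS or pneumonia. The figure also omits unventilated patients on vasopressors, who are the clearest affected cases. It bounds nothing.
- **That items iii and iv contradict each other.** Item iii covers "Chronic lung disease without suspected infection, aspiration, or inflammation" and item iv lists "Asthma, COPD, sarcoidosis, interstitial lung disease, neuromuscular respiratory failure" without a qualifier. A reader might infer that a COPD patient newly on non-invasive ventilation for a viral infection is barred by item iv. But the items are examples under a stem about the suspected cause, not bars on a comorbidity. Section 7.2.2 gives suspected infection with a SOFA score of at least 2 as a common form of Sepsis-3, and respiratory dysfunction can supply those points. Such a patient would ordinarily be suspected sepsis and fall outside the stem.

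**Conclusion.** The point holds in a limited form. Exclusion 11 as worded bars patients whose dysfunction is attributed to a non-infectious inflammatory condition admitted by inclusion 4 when none of the three syndromes is yet suspected. Inclusion 4 and sections 6 and 7.1.3 say that this group is to be enrolled. The conclusion assumes that sites screen on the literal criteria and that exclusions take precedence, as section 7.1.2 states.

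The number affected cannot be derived from the protocol, so nothing can be said about the effect on the 4,000 participants or on the syndrome targets. The intent is recoverable from the rationale, and patients with a suspected syndrome are untouched. This is a correction to eligibility wording, worth making because it is cheap and governs who enters the cohort, but it does not threaten the study.

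**What to change.** Reconcile inclusion 4, exclusion 11 and section 7.1.3 by amending the stem of exclusion 11. In line with the protocol's own rationale, an alternative condition would be one other than ARDS, pneumonia, sepsis, or an acute inflammatory condition that qualifies under inclusion 4 and the second goal of section 7.1.3. The same sentence should state that the conditions in items i to xi, with the qualifiers given there, remain excluded. Without that statement the open-ended wording of inclusion 4 would let a site argue that a listed condition, such as cytokine release syndrome, is exempt.

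Add a field to the eligibility form for the qualifying inclusion 4 condition, so that case mix can be examined by site.

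Items iii and iv should not be merged under one qualifier, because that could change the population. The sponsor may wish to clarify how the two items relate.

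The cost is a protocol amendment of one or two sentences, a memo to sites and one form field. Sites that have applied the stem literally may then enrol a somewhat larger share of non-infectious patients.

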7.1.3 Rationale for eligibility criteria

The goal is to enroll patients with acute cardiopulmonary dysfunction that is due to either (a) ARDS, pneumonia, or sepsis, or (b) an acute inflammatory condition that places patients at high risk for short-term development of ARDS, pneumonia, or sepsis. Patients with common critical care conditions that may result in acute cardiopulmonary dysfunction, but which have established pathophysiologic mechanisms distinct from ARDS, pneumonia, and sepsis will be excluded. This approach will optimize the ability to understand the pathophysiology of ARDS, pneumonia, and sepsis, whereas an approach that limited enrollment to patients who meet the historical syndrome definitions would limit our ability to identify new, meaningful phenotypes. In addition, this approach recognizes the difficulty in making definitive clinical diagnosis of historical syndromes (ARDS, pneumonia, and sepsis) at the time of enrollment among critically ill patients. By taking this approach to inclusion criteria, the APS Consortium is expected to further improve our ability to make diagnoses in real time.

Potential participants of all sexes, genders, races, ethnicities, language proficiencies, and nationalities are invited to participate. Enrollment in the cohort will not be limited by the language(s) spoken by the

participant. Individual components of APS studies, such as long-term outcome surveys, may be limited to participants who speak certain languages to ensure adequacy of data collection for those components. All adult patients across the age span are invited to participate; pediatric participants are not the focus of this project and will not be enrolled.

Pregnant individuals are eligible to participate in the APS cohort because pregnant patients experience APS syndromes at rates higher than the general population of similar age, and there is no strong rationale to exclude such participants. The risks of the procedures in this study are not greater for pregnant participants than for other participants. Due to potential risks to a fetus posed by study procedures that are greater than minimal risk, study procedures for pregnant participants will be limited to procedures that are not greater than minimal risk. The altered schedule of procedures for pregnant participants is detailed in the schedule of events section of this protocol.

Prisoners are excluded because there is concern that their participation may not be fully voluntary.

Patients who are unable to consent for themselves due to acute illness, cognitive impairment, or psychological impairment are eligible to participate. Details of inclusion of these patients are included in the Human Subjects section of this protocol.

Pediatric participants <18 years old are excluded because they are frequently admitted to different, specialized pediatric hospitals, the tools for assessing organ dysfunction and molecular phenotyping are different for children, and the focus of this study is on adults.

7.2 Anticipated Study Population

7.2.1 Enrollment targets

The APS Consortium investigators recognize that phenotyping efforts require adequate numbers of patients within specific groups for which phenotyping is desired. Additionally, care will be taken to promote representation among multiple sociodemographic groups. The APS Consortium recognizes three key priorities for representation: (1) sociodemographic representation, (2) distribution across the historical syndromes of ARDS, pneumonia, and sepsis, and (3) patients in whom deep respiratory samples are available (patients ventilated through an endotracheal tube).

The APS Consortium Steering Committee will regularly monitor participant characteristics of the overall cohort and the subset with in-person long-term outcome visits to promote adequate representation of several groups. The Steering Committee will work to achieve the following goals:

- i. Adequate race, ethnicity, and sex representation, including inclusion of participants reporting Black race or Hispanic ethnicity at or above percentages reported for these groups in US census data;
- ii. Adequate representation from rural areas, based on urban-rural classifications by the US Census Bureau following the 2020 census. A rural area is defined as any area in the US outside the 2,646 recognized urban areas. An urban area is defined as a census area with >2,000 housing units

or >5,000 population. A list of urban areas is available upon request. US Census Bureau definitions of urban and rural are available at: <https://www.census.gov/programs-surveys/geography/guidance/geo-areas/urban-rural.html>;

- iii. Adequate representation from the historical ARDS, pneumonia, and sepsis categories, with at least 1000 patients with ARDS, 2000 patients with sepsis, and 2000 patients with pneumonia in the overall cohort, recognizing that a given patient may count toward multiple categories;
- iv. Adequate numbers of patients who received invasive mechanical ventilation in the overall cohort (target: ≥ 1000 patients) and long-term outcome subset (target: ≥ 150 patients).

The APS Steering Committee will review participant characteristics of the enrolled cohort overall and by site no less frequently than every 3 months (quarterly) during the enrollment period. This review will include data tables that display participant characteristics for the following categories:

- Sociodemographics, including race, ethnicity, and sex
- Home location (zip code used for rural/urban classification)
- Distribution of historical syndromes (ARDS, pneumonia, sepsis)
- Use of invasive mechanical ventilation during the index hospitalization

After reviewing these quarterly data, the APS Steering Committee will develop an action plan for enrollment for the next quarter (Table 3). Specific action plans will be developed in response to data on characteristics of participants enrolled during the last quarter and overall in the study, and the effect that prior action plans had on enrollment. Data tables showing participant characteristics and the APS Steering Committee action plan for enrollment in the next quarter will be submitted to the APS Observational Study Monitoring Board (OSMB) each quarter. After reviewing the data tables and action plan, the OSMB may issue further guidance and/or call an ad hoc meeting among the OSMB, NIH, and APS Consortium investigators to discuss and revise the action plan.

Table 3. Potential action plans to alter enrollment practices in response to observed quarterly enrollment data.

Specific action plans will be developed by the APS Steering Committee in response to data. Hypothetical examples are shown in this table.

Observed Data	Potential Action Plan
The proportion of participants with Black race is below the proportion of adults in the US census with Black race.	Provide study teams at sites with a high proportion of Black patients with additional training on consent practices and enrolling patients with alteration of informed consent procedures. If it is found that patients with Black race report an aversion to particular study procedures (such as stool samples or post-discharge surveys), the steering committee may consider dropping these study procedures. The APS Coordinating Center will work with the Clinical Center principal investigator for sites with a large population of Black patients to try to ensure funds are available for optimizing staffing of the enrollment teams at those sites. Adding sites to the consortium that care for a large number of Black patients could be an option if additional funds become available.
The proportion of participants with Hispanic ethnicity is below the proportion of adults in the US census with Hispanic ethnicity.	Provide study teams at sites with a high proportion of Hispanic patients with additional training on consent practices and enrolling patients with alteration of informed consent. Study materials, including consent forms and surveys, will be available in Spanish. The coordinating center will ensure study teams understand these Spanish language documents. If it is found that patients with Hispanic ethnicity report an aversion to particular study procedures (such as stool samples or post-discharge surveys), the steering committee may consider dropping these study procedures. The APS Coordinating Center will work with the Clinical Center principal investigator for sites with a large population of Hispanic patients to try to ensure funds are available for optimizing staffing of the enrollment teams at those sites, including the availability of Spanish interpreters. Adding sites to the consortium that care for a large number of Hispanic patients could be an option if additional funds become available.
The proportion of participants with a rural home zip code is below the proportion of adults in the US census with a rural home zip code.	Provide study teams at sites with a high proportion of rural patients with additional training on consent practices and enrolling patients with alteration of informed consent procedures. If it is found that patients from rural zip codes report an aversion to particular study procedures (such as stool samples or post-discharge surveys), the steering committee may consider dropping these study procedures. The APS Coordinating Center will work with the Clinical Center principal investigator for sites with a large rural population to try to ensure funds are available for optimizing staffing of the enrollment teams at those sites. Adding sites to the consortium that care for a large number of rural patients could be an option if additional funds become available.
Less than 25% of enrolled participants have ARDS.	Change eligibility criteria so fewer patients with mild lung injury and no lung injury are enrolled. Potential protocol changes include requiring hypoxemia for enrollment (removing the path for eligibility based on vasopressor use only without hypoxemia) and increasing the threshold for supplemental oxygen for eligibility (for example, increasing from 6 lpm to 10 lpm).

